5.5.1. Dosage Preparation and administration of study vaccine

The powder and suspension should be inspected visually for any foreign particulate matter and/or variation of appearance. If either is observed, do not reconstitute the vaccine.

How to prepare Shingrix:

Shingrix must be reconstituted prior to administration.

- 1. Withdraw the entire contents of the vial containing the suspension into the syringe.
- 2. Add the entire contents of the syringe into the vial containing the powder.
- 3. Shake gently until the powder is completely dissolved.

The reconstituted vaccine is an opalescent, colourless to pale brownish liquid.

The reconstituted vaccine should be inspected visually for any foreign particulate matter and/or variation of appearance. If either is observed, do not administer the vaccine.

After reconstitution, the vaccine should be used promptly; if this is not possible, the vaccine should be stored in a refrigerator $(2^{\circ}C - 8^{\circ}C)$. If not used within 6 hours it should be discarded.

Before administration:

1. Withdraw the entire contents of the vial containing the reconstituted vaccine into the syringe.

2. Change the needle so that you are using a new needle to administer the vaccine.

Any solution in excess of 0.5mL should be expelled. After confirming that the needle is not in a blood vessel, the reconstituted vaccine should be administered by IM injection, preferably into the deltoid muscle of the non-dominant upper arm, using a standard aseptic technique. The injection site should be on the same arm for all injections for an individual subject. In rare situations when there is no other alternative, the second injection may be given on the different arm.

Contraindications to subsequent vaccination

The following events constitute absolute contraindications to further administration of the vaccine. If any of these events occur during the study, the subject must not receive additional doses of vaccine but may continue other study procedures at the discretion of the investigator.

• Anaphylaxis following the administration of vaccine(s);

• Acute disease and/or fever at the time of vaccination. – Fever is defined as temperature \geq 37.5°C (99.5°F) on oral, axillary or tympanic setting. The preferred route for recording temperature in this study will be oral. Subjects with a minor illness (such as mild diarrhoea, mild upper respiratory infection) without fever can be administered all vaccines.

5.6. Concomitant Medication

At each study visit/contact, the investigator should question the subject about any medication taken and vaccination received by the subject. Concomitant medication must be recorded in the log.

For management of concomitant therapies, please refer to the SmPC. A complete listing of all concomitant medication received during the treatment phase must be recorded in the relevant CRF.

6. Selection and Withdrawal of Participants

6.1. Inclusion Criteria

- 1. Able and willing to comply with the requirements of the protocol.
- 2. Able and willing to provide fully informed consent.
- 3. Male or non-pregnant, non-lactating females.
- 4. People living with HIV ≥50 years **OR** have perinatally acquired HIV and are aged 18 and over.
- 5. If female, of child-bearing age, not sterilised and participating in sexual intercourse that could result in pregnancy, using at least 1 acceptable method of contraception when engaging in sexual activities that can result in pregnancy, beginning at screening through month 4. Acceptable methods of contraception include the following:
 - Hormonal contraception.
 - Male or female condom.
 - Diaphragm or cervical cap with a spermicide.
 - Intrauterine device.

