4.6. Trial Assessment Schedule for Investigators (Table 1)

Visit number	1	2	3	4	5	6	7
	Screening*	Baseline					
Week number (window period)		0 (+ 8 weeks)	4 (+/-3 weeks)	8 (+/- 3 weeks weeks)	12 (+/-3 weeks)	24 (+/-3 weeks)	48 (+/-3 weeks)
Written informed consent	Х						
Eligibility assessment	Х	Х					
Demographics	Х						
Medical History	Х						
Vital Signs	Х	Х	Х	Х			
Temperature	Х	Х		Х			
Full Physical Exam	Х						
Directed Physical Exam		Х	Х	Х	Х	Х	Х
Concomitant medications	Х	Х	Х	Х	Х	Х	Х
Adverse events unsolicited AEs and SAEs and IMD review	х	х	х	х	х	х	х
Vaccination		Х		Х			
Solicited general Adverse Events (Table 3)			х		х		
Survey		Х					
Urine pregnancy test**	х	Х		х			
CD4 (CD4:CD8)		х					х
HIV viral load		Х				Х	Х
Hepatitis BsAg		Х					
Safety blood samples FBC, U&E, ALT		х				х	х
Blood samples for Immunology analysis		х	Х	Х	Х	Х	Х
Blood samples for Serology analysis		Х	Х	Х	Х	Х	х

*screening and baseline can occur on the same day

**Pregnancy test must be performed even if the subject is menstruating at the time of the study visit.

Table 2: Procedures to be performed for each suspected HZ case

Clinical history

Perform clinical examination

Collect samples from all sites with clinical suspicion of HZ (eg skin, CSF, vitreous fluid). The following samples should be taken from each site (there may be more than one site per person presentation.

- 1 swab to local lab for VZV PCR

- 1 swab to GOSH/University College London

Record relevant clinical information regarding HZ in eCRF by study staff/investigator including

- Date of onset of symptoms
- Location of symptoms
- Severity of symptoms
- Signs

Blood sample: ACD and SST tubes to be sent to Imperial College London laboratory (From Guys and St Thomas' NHS Foundation Trust or Imperial College NHS Healthcare Trust) or University of Oxford (from Oxford University Hospitals NHS Foundation Trust)

5. Trial Medication

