5.3. IMP Risks

The Reference Document is the Summary of Product Characteristics (SmPC). The latest SmPC published for the UK is

https://www.medicines.org.uk/emc/product/12054/smpc#gref.

The vaccine is administered intramuscularly.

Syncope (fainting) can occur following, or even before, any vaccination as a psychogenic response to the needle injection.

In adults aged \geq 50 years, the most frequently reported adverse reactions were pain at the injection site (68.1% overall/dose; 3.8% severe/dose), myalgia (32.9% overall/dose; 2.9% severe/dose), fatigue (32.2% overall/dose; 3.0% severe/dose) and headache (26.3% overall/dose; 1.9% severe/dose). Most of these reactions were not long-lasting (median duration of 2 to 3 days). Reactions reported as severe lasted 1 to 2 days.

In adults \geq 18 years of age who are immunodeficient or immunosuppressed due to disease or therapy (referred to as immunocompromised (IC)), the safety profile was

consistent with that observed in adults 50 years and over. There are limited data in adults aged 18-49 years at increased risk of HZ who are not IC.

Female participants of childbearing potential have to practice adequate contraception from 30 days before vaccination until 2 months after dose two and had to have a negative pregnancy test on the days of both vaccinations, prior to injection.

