6.2. Exclusion Criteria

- 1. Active herpes zoster disease in past 6 months preceding the first dose of study vaccine
- 2. If female, planning to get pregnant, currently pregnant (evidence from positive serum or urine pregnancy test), or breastfeeding.
- 3. Used any investigational or non-registered product other than the study vaccine within 30 days preceding the first dose of study vaccine or planned use during the study period.
- 4. Vaccinated within the 12 months preceding the first dose of study vaccine or planned to be vaccinated during the study with a (non-study) vaccine against herpes zoster or varicella zoster virus.
- 5. History of any reaction or hypersensitivity likely to be exacerbated by any vaccine component.
- 6. Received or planned to receive a live vaccine in the period starting 30 days before the first dose of study vaccine and ending 30 days after the last dose

of study vaccine or had received or planned to receive a non-replicating vaccine within 8 days before or within 14 days after either dose of study vaccine.

- 7. Acute disease and/or fever at the time of enrolment; Fever is defined as temperature ≥ 37.5°C (99.5°F) on oral, axillary or tympanic setting. The preferred route for recording temperature in this study will be oral. Subjects with a minor illness (such as mild diarrhoea, mild upper respiratory infection) without fever may, be enrolled at the discretion of the investigator.
- Chronic administration (defined as more than 15 consecutive days) of immunosuppressants or other immune-modifying drugs within six months prior to the first vaccine dose. For corticosteroids, this will mean prednisone < 20 mg/day, or equivalent, is allowed. Inhaled and topical steroids are allowed.

Drugs include: Chemotherapeutic drugs, Immunomodulators and systemic immunosuppressive treatments, Oral glucocorticoids >20 mg/day, Cyclosporine, Methotrexate, Interleukins and/or cytokines, Immunotherapies (including TNF blockers).

- 9. Any other clinical condition that, in the opinion of the investigator, might pose additional risk to the subject due to participation in the study.
- 10. History of potential immune-mediated disease (pIMD). Note: If the subject has any condition on the list of pIMDs specified in the protocol, they must be excluded unless the aetiology is clearly documented to be non-immune mediated.

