7.1. By Visit

This prospective multicentre study will recruit up to 70 individuals attending HIV services. Individuals will attend for visits at screening, baseline (vaccination), week 4, week 8 (vaccination), week 12, week 24 and week 48. Research and safety bloods will be taken at each visit. Study participants will receive 2 intramuscular doses of HZ/su 2 months apart. Vaccine reactogenicity review will occur 15 minutes post vaccination.

Any individual who develops shingles after vaccination will have swabs taken for viral diagnosis and viral sequencing.

The trial assessment schedule consists of a screening visit (visit 1) followed by an enrolment visit which defines week 0 (visit 2). If preferred by the participant, both visits can occur on the same day.

The first injection will take place at week 0 (visit 2) and the second injection visit is at week 8 (visit 4). Follow-up visits to ask about all adverse events and take blood are at weeks 12, 24 and 48 (visits 5,6,7). Additional visits may be undertaken if indicated, for example to investigate or follow-up an adverse event or abnormal laboratory result or if a participant develops symptoms suggestive of shingles.

The required volumes per visit together with sample collection and processing guidelines are described in detail in the laboratory manual. Required volumes of samples analysed by local laboratories (i.e. safety and HIV parameters) might vary according to local standard procedures. The visit windows are defined in the in Table 1.

Biological samples to be collected: -

Blood samples will be collected from all subjects at every visit to evaluate safety and/or immunogenicity. Should the participant experience a suspected HZ episode, swabs from the lesion and a blood sample will be collected.

Study details: Study subjects will be provided with a subject card which contains the address and telephone number of the main contact for information about the trial. The aim of this card is to inform any physician having to deal with a subject in an emergency situation that the subject is in a clinical trial and that he/she can contact the trial investigator for more relevant information. Subjects must be instructed to keep these cards in their possession at all times.

Study Assessments and Procedures

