Refer to the Table 1, for the visit schedule. Note that unscheduled visits may be required. Immediate safety concerns should be addressed by the PI as soon as he or she becomes aware of the concern to determine if the participant should continue or discontinue study vaccination. The PI will inform the Sponsor immediately upon occurrence or awareness. Adherence to the study design requirements, including those specified in the visit schedule, is essential and required for study conduct. All participants will be enrolled and followed up for 48 weeks. The vaccination phase will last 8 approximately weeks.

Procedures prior to study participation

Potential participants will be identified through HIV clinics. Eligible individuals will be informed about the trial and given a patient information sheet at least one day prior to consent is taken which explains the aims, methods, and potential benefits and hazards of the trial.

Screening visit

The study staff conducting the Screening visit will:

- Introduce themselves and their role to the participant and confirm the identity of the participant.
- Confirm that the means of contact is adequate to conduct the contact/visit

• Participants will be provided with the study information, including the participant information sheet (PIS) to read. They will discuss the study with a member of the research team in person or remotely. Consent will be obtained by an investigator.

After informed consent has been collected, a unique trial identifier will be assigned by the study staff. The screening visit will conduct:

- Eligibility assessment (as per inclusion/exclusion criteria)
- Demographics recording
- Medical History
- Vital signs
- Temperature

- Full physical exam
- Urine pregnancy test (women of childbearing potential only)
- Concomitant medications review
- Adverse Events Review

Procedures prior to the first vaccination at enrolment visit

Screening and enrolment can occur on the same day. If not, the enrolment visit should take place within 8 weeks following the screening visit. If more than 8 weeks have elapsed study repeat the screening assessments.

Study staff will review information related to eligibility collected at screening and determine whether there are any clinically relevant abnormalities that require further investigation prior to enrolment.

Baseline, Week 0 (+8 weeks)

The baseline visit will conduct:

- Eligibility Assessment (as per inclusion/exclusion criteria)
- Vital signs
- Temperature

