- Directed physical exam
- Concomitant Medication review
- Vaccination
- Vaccine reactogenicity, unsolicited adverse event & IMD review
- Participant survey: beliefs about shingles and shingles vaccines
- Urine pregnancy test (women of childbearing potential only)
- Venepuncture for:
 - CD4 (CD4:CD8)
 - o HIV Viral Load
 - o Hepatitis BsAg
 - Safety blood sample (FBC, U&E, ALT)
 - Immunology blood sample
 - Serology blood sample

Note: Pregnancy test will be performed even if the subject is menstruating at the time of the study visit. The study vaccine can only be may only be administered if the pregnancy test is negative.

Check contraindications to vaccination: Contraindications to vaccination are to be checked at the beginning of each vaccination visit. Furthermore, any subject with a clinically diagnosed HZ episode between Visit 1 and Visit 2 should receive the second vaccination 3 months after the day of onset of shingles.

Vaccination Visits: 2 (Baseline) & 4

Prior to injection, study staff will conduct an inspection of the site where injections will be administered in each arm as part of the directed physical examination. The axillary, oral or tympanic body temperature of all subjects will be measured prior to any study vaccine administration. The preferred route for recording temperature in this study will be oral. All vaccines may be administered to persons with low-grade fevers, i.e., oral, tympanic on oral setting, or axillary temperature < 37.5°C. If a subject has an axillary/oral/tympanic on oral setting temperature \geq 37.5°C, it will constitute a contraindication to administration of vaccine.

Study staff should administer the injection into the deltoid muscle of the designated upper arm and record this in the appropriate CRF including the time of injection.

The Shingrix vaccine dose, after reconstitution, is 0.5 ml in volume and should be injected into the deltoid muscle of the non-dominant arm. Following injection participants should remain in clinic, in order to assess vaccine reactogenicity and solicited adverse events at 15 minutes following injection.

If the Investigator or delegate determines that the health on the day of vaccination temporarily precludes vaccination, the visit will be rescheduled within the window period for this visit.

The vaccinees will be observed for 15 minutes, with appropriate medical treatment readily available in case of anaphylaxis, following the administration of vaccine.

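### Inclusion criterion 5 sets a shorter contraception period than section 5.3: none of the 30 days before dose 1 is assured with same-day screening, and, counted from week 0, it ends about 2.3 weeks early if dose 2 is given at week 11

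*Protocol*

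**What the plan says.** Two sections of the protocol fix the contraception period, and they differ.

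- Section 5.3 (IMP Risks), for female participants of childbearing potential: "adequate contraception from 30 days before vaccination until 2 months after dose two", with a negative pregnancy test on each vaccination day.
- Section 6.1, inclusion criterion 5: at least one acceptable method, "beginning at screening through month 4". The origin of month 4 is not stated.

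The timing rules that bear on this are:

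- Section 4.6, Table 1 footnote: "screening and baseline can occur on the same day". Section 7.1 repeats this and adds that otherwise "the enrolment visit should take place within 8 weeks following the screening visit".
- Section 4.6, Table 1, dose 2 visit: "8 (+/- 3 weeks weeks"), so dose 2 may be given up to week 11.
- Section 7.1 states "The visit windows are defined in the in Table 1", but its own entry for visit 4 gives week 8 with a window of minus 4 to plus 7 weeks, so up to week 15.

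The safeguards are:

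- Section 6.2, exclusion 2, excludes a woman on these grounds among others: "If female, planning to get pregnant, currently pregnant".
- Section 7.1, baseline: "The study vaccine can only be may only be administered if the pregnancy test is negative".
- Table 1 schedules pregnancy tests at screening, baseline and week 8, and none later.

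**The concern.** Sites screen against the eligibility list; the visit procedures in section 7.1 direct staff to assess eligibility by the inclusion and exclusion criteria. The longer period sits in a section on product risks. A site that follows criterion 5 to the letter can therefore enrol and follow a woman in a way that section 5.3 does not allow.

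At the start, a woman who begins contraception on the day of a combined screening and baseline visit satisfies criterion 5 with none of the 30 days. A woman already using a method may well have that cover, but the criterion does not ask. At the end, a fixed month 4 cannot follow a second dose whose date is allowed to move.

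Late second doses are foreseeable. Section 3 explains that the windows were made wide because young people with perinatally acquired HIV find regular attendance difficult. That group is enrolled from age 18 and is where women of childbearing potential are most likely to be found. At stake are a gap in participant protection and a source of avoidable protocol deviations.

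**Working it through.** **Inputs**

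- Required period (section 5.3): from day -30 to dose 2 plus 2 months.
- Criterion 5 period (section 6.1): from screening to month 4.
- Screening to dose 1: 0 days up to 8 weeks (Table 1 footnote, section 7.1).
- Dose 2: planned at week 8 (section 5.2); latest week 8 + 3 = 11 (Table 1) or 8 + 7 = 15 (section 7.1 visit entry).
- Assumptions: month 4 is counted from week 0, and 1 month = 365.25 / 12 / 7 = 4.348 weeks. Both are varied below.

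**Start**

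Days not assured = max(0, 30 - days from screening to dose 1).

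- Same day: 30 - 0 = 30 days not assured, so 0 of 30 covered.
- 14 days apart: 30 - 14 = 16 days not assured.
- 30 days or more apart: none.

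**End**

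Criterion 5 ends at 4 × 4.348 = week 17.39. The section 5.3 period ends at the week of dose 2 + 2 × 4.348 = week of dose 2 + 8.70. Shortfall = section 5.3 end minus criterion 5 end.

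| Dose 2 | Section 5.3 end | Criterion 5 end | Shortfall |
|---|---|---|---|
| Week 8 (planned) | 16.70 | 17.39 | none (0.70 weeks to spare) |
| Week 11 (Table 1 limit) | 19.70 | 17.39 | 2.30 weeks (16 days) |
| Week 15 (section 7.1 limit) | 23.70 | 17.39 | 6.30 weeks |

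The first row shows that month 4 does follow from section 5.3 on the planned schedule, and only there. Break-even is dose 2 at 17.39 - 8.70 = week 8.70, about 5 days late.

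**Sensitivity**

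- With 28-day months, month 4 is week 16. The shortfall is 8 + 8 - 16 = 0 at week 8, 11 + 8 - 16 = 3.0 weeks at week 11, and 15 + 8 - 16 = 7.0 weeks at week 15.
- If month 4 is counted from screening, each figure worsens by the screening-to-baseline interval. At the maximum of 8 weeks, calendar months and dose 2 at week 11 give 2.30 + 8 = 10.30 weeks.

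**Overlap with the primary endpoint**

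The latest week-12 visit under Table 1 is 12 + 3 = week 15. The end gap opens at week 16 (28-day months) or week 17.4 (calendar months) when counted from week 0, so after that visit.

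**The case against.** The best case against is that the two texts are compatible. Inclusion criterion 1 requires participants to be able and willing to comply with the protocol, section 5.3 is part of it, and applying the longer period satisfies both. Month 4 also reads naturally as shorthand for 2 months after a dose at month 2. The end gap is partial: with dose 2 at week 11, criterion 5 still gives 17.39 - 11 = 6.39 of the 8.70 weeks. At the start, same-day screening is optional, women planning pregnancy are excluded, and a negative test is required before each dose. The product is a subunit vaccine in a trial classed as low risk, and section 3 favours lighter contraception rules.

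Much of this stands as context. The shortfall is conditional, it vanishes on the planned schedule, and the safeguards lower the risk. It does not remove the conflict. A general duty to comply does not tell a site which of two stated periods governs, and it cannot create cover before a same-day screening visit. Section 5.3 requires the tests in addition to contraception, and none is scheduled after dose 2, when the end gap opens. The remark in section 3 concerns double contraception, that is, the number of methods rather than the duration; criterion 5 already asks for only one method.

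**Conclusion.** The concern holds. Criterion 5 is weaker than section 5.3 at both ends, and a site can meet the first while breaching the second.

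- Start: 0 of 30 days assured with same-day screening; no gap if screening is at least 30 days before dose 1.
- End: 2.3 weeks short at the Table 1 limit with calendar months from week 0 (3.0 with 28-day months), 6.3 weeks at the conflicting section 7.1 limit, and no shortfall with dose 2 at week 8.

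The existence of the discrepancy does not depend on any assumption. The size at the end depends on the origin of month 4 and the length of a month. Counting from week 0 is the milder reading, because counting from screening can only widen the gap. The protocol does not give the number of women affected, and no loss from the primary analysis is claimed. This should be corrected, but it does not threaten the trial's validity.

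**What to change.** **End.** Reword criterion 5 so that contraception continues until 2 months after the date on which dose 2 is actually given. This removes the dependence on the origin of month 4, on the length of a month and on which visit window applies.

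**Start.** The sponsor should choose one of two options:

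- (a) Add to criterion 5 at least 30 days of contraception before dose 1. Some women could then not be screened and vaccinated on the same day.
- (b) Amend section 5.3 to start at screening, with a negative pregnancy test before each dose. Same-day visits stay open to all, but the 30-day lead-in is given up and protection before dose 1 rests on the test. This is the weaker option, because it lowers the requirement to match the looser text.

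**Cost.** Wording in section 6.1, in section 5.3 under option (b), and in the information sheet if it repeats the period. The synopsis states no period and needs no change.
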